## Study aim

The trial is aimed at verifying the superiority of a sensor-augmented pump (SAP) system, in comparison with optimized multiple daily injections (MDI) of insulin, using degludec as basal insulin, with respect to glycemic control, incidence of severe hypoglycemia, body weight, local reactions, treatment satisfaction, and patient preferences.

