## Study endpoints

The **primary endpoint** is the superiority of SAP versus MDI on HbA1c.

**Secondary endpoints** include:

- 1) Severe hypoglycemia
- 2) Change in body weight
- 3) Local reactions on the site of insulin administration and/or monitoring of glucose
- 4) Treatment satisfaction, measured using the Italian validated version of the WHO Diabetes Treatment Satisfaction Questionnaire.
- 5) Patients' preference for either treatment

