## Study design

The study is designed as a single-center, open-label, cross-over randomized trial.

Lo studio è disegnato come un trial randomizzato in cross-over, in aperto.

After verification of inclusion and exclusion criteria, enrolled patients will be randomized (using a computer-generated random number sequence) 1:1 to either SAP or MDI for 4 months, and then switched to the alternative treatment.

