## Treatments

- **MDI:** multiple daily injections of insulin, using degludec as basal insulin and lispro, aspart or glulisine as prandial insulin. Dose adjustments will be performed on the basis of self-monitoring of capillary blood glucose (standard of care).
- **SAP:** Sensor augmented pump Vibe Animas Platinum integrated with glucose sensor Dexcom G4. Patients will be educated to manage glucose excursions detected by the sensor, and instructed to download sensor and pump data before each planned visit.

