## Duration of the study

- *Duration of enrolment:* 18 months
- *Duration of treatment:* 4 months for each treatment phase, with no wash-out.

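### No section of the protocol plans to record ketoacidosis, severe hyperglycemia with ketosis, or insulin-delivery failure by treatment phase, so the comparison of acute metabolic harms is one-sided

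*Combined protocol and SAP*

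**What the plan says.** The Study aim section sets out superiority of SAP (sensor-augmented pump) over MDI on "glycemic control, incidence of severe hypoglycemia, body weight, local reactions, treatment satisfaction, and patient preferences". Under Study endpoints, the primary endpoint "is the superiority of SAP versus MDI on HbA1c". The secondary list opens with "Severe hypoglycemia" and also holds body weight, "Local reactions on the site of insulin administration and/or monitoring of glucose", treatment satisfaction and preference.

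The Treatments section defines MDI as injections "using degludec as basal insulin and lispro, aspart or glulisine as prandial insulin", and the other treatment as "Sensor augmented pump Vibe Animas Platinum integrated with glucose sensor Dexcom G4". Study design randomizes patients "1:1 to either SAP or MDI for 4 months, and then switched to the alternative treatment", so every patient who completes the trial has one phase on the pump. Duration of the study gives "4 months for each treatment phase, with no wash-out".

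The Statistical plan applies the primary-endpoint methods (paired t tests, a repeated-measures regression, LOCF for missing data) to the secondary endpoints. It contains no separate safety analysis. Ketoacidosis, ketosis, severe hyperglycemia, pump or infusion-set failure and general adverse-event collection are not mentioned in any section supplied.

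**The concern.** Under MDI the basal insulin is a long-acting injection. In the SAP phase a pump delivers the insulin, so an interruption of delivery can leave a patient with type 1 diabetes without basal cover. The acute harm that can follow is ketosis or ketoacidosis. This is general clinical reasoning from the contrast being tested; the documents do not discuss it.

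The plan counts the acute harm on which it hopes to show SAP superior, and is silent on the acute harm that a delivery failure could cause. The trial could then report superiority on HbA1c and severe hypoglycemia while episodes of ketoacidosis, in either phase, enter no comparison. Events not recorded by phase during the trial may not be recoverable afterwards.

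**Working it through.** **1. Can a listed outcome stand in for the missing one?**

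- *HbA1c.* It is an average over weeks. An episode of two days (an assumed length) is 2/120 = 1.7% of a phase of about 120 days.
- *Severe hypoglycemia.* This is the opposite event.
- *Local reactions.* These cover skin sites, not metabolic consequences.
- *Analysis sets.* If a patient leaves the pump after an episode, LOCF fills the missing outcome from an earlier value, and the per-protocol set drops patients not on the planned treatment. The episode itself appears in neither analysis.

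No listed outcome captures the event.

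**2. Exposure.** The plan gives no figure of its own for this harm. The inputs are 27 patients (Statistical plan) and 4 months per phase (Duration of the study):

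27 x 4/12 = 9 patient-years per treatment, if all patients complete both phases.

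**3. Chance of seeing an event.** The documents give no rate, so the rates r below are assumptions. Expected events = 9r; P(at least one) = 1 - exp(-9r).

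| Assumed rate per 100 patient-years | Expected events in one phase | P(at least one) |
|---|---|---|
| 1 | 0.09 | 9% |
| 2 | 0.18 | 16% |
| 5 | 0.45 | 36% |
| 10 | 0.90 | 59% |

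**4. What zero events would show.**

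- One-sided 95% upper limit: -ln(0.05)/9 = 0.33 per patient-year, or 33 per 100 patient-years.
- Upper end of the two-sided 95% interval: -ln(0.025)/9 = 0.41 per patient-year, or 41 per 100.
- As a share of patients, one-sided: 1 - 0.05^(1/27) = 10.5%.

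**5. Could the phases be formally compared?** With equal exposure and no treatment difference, each event (taken as independent) falls in either phase with probability 1/2. If all of k events fell in one phase, the two-sided exact p-value is 2 x 0.5^k. For k = 5 this is 0.063 and for k = 6 it is 0.031. At least six events, all in one phase, would be needed; that is 6/9 = 67 per 100 patient-years in that phase, far above the rates tabulated. The outcome can only be descriptive.

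**The case against.** Several points on the other side stand.

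- The secondary list is introduced with open wording, and one part of the document was not available for review. The supportable statement is that no supplied section plans this outcome. A reader might infer that the listed endpoints are exhaustive and exclude it; the text does not say so.
- A reader might infer that the whole harm comparison favours SAP. It does not: local reactions at infusion and sensor sites are an endpoint and can count against SAP. The one-sidedness is confined to acute metabolic harms.
- A reader might infer that ketoacidosis is expected to rise on this system. The documents give no rate and no direction. Entry requires HbA1c below 8.0% and at least four daily self-tests, and SAP patients are taught to manage excursions seen on the sensor. Delivery failure is a plausible mechanism, not a documented increase.
- A reader might add that weight lost in an episode would flatter SAP on body weight. Nothing supplied shows that such a loss would persist to the end of a phase or move a mean of 27 patients.
- The plan announces no overall benefit-harm conclusion, and leaving out one outcome does not bias the others.
- At 1, 2 or 5 events per 100 patient-years, zero is the likeliest count.
- Adding a secondary endpoint without amending the Statistical plan would send it to paired t tests and LOCF. Continuous sensor data in one phase only could also make ascertainment unequal in an open-label trial.

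These points limit the claim and shape the remedy. They do not supply the missing record: without planned collection, the report could say nothing dependable about these events in either phase.

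**Conclusion.** The concern holds in limited form. The supplied text plans no collection or reporting by phase of ketoacidosis, severe hyperglycemia with ketosis, or delivery failure, in a trial whose contrast replaces injected basal insulin with a pump. The named acute metabolic harms therefore cover one direction only. The primary test and the severe-hypoglycemia comparison are unaffected, and the size of any imbalance cannot be computed from the documents.

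The calculable part is the amount of information: 9 patient-years per treatment, assuming full follow-up and a constant (Poisson) event rate. That is enough for an event to be plausible at the assumed rates and too little for a formal comparison. Absence of reported events would not be evidence of safety. The change should be made because it is cheap and the information may be lost otherwise.

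**What to change.** 1. **Study endpoints.** Add a descriptive safety outcome: *ketoacidosis, and severe hyperglycemia with ketosis, including episodes due to pump or infusion-set failure*. Give it one pre-specified definition for both phases, for example episodes needing medical care or hospital treatment. A definition of that kind does not depend on sensor data and adds no ketone testing.
2. **Collection.** Ask the same question at the planned visits in both phases. Collect it for all randomized patients, including those who stop a treatment, and attribute each event to the treatment in use at onset. The attribution rule matters because there is no wash-out.
3. **Statistical plan.** Exempt this outcome from the paired t test and LOCF. Report counts and rates per patient-year by treatment, with exact 95% confidence intervals and no test.
4. **Interpretation.** State in advance that about 9 patient-years per treatment cannot support a formal comparison, and that zero events would leave a one-sided 95% upper limit of about 33 per 100 patient-years.

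**Cost.** One endpoint line, one case-report-form item and a short addition to the Statistical plan. The sample size and primary test do not change. This assumes comparable visits in both phases; the supplied text mentions planned visits but gives no schedule. The downsides are few events, a wide interval, and no count of milder episodes that never reach medical care.

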## Study endpoints

The **primary endpoint** is the superiority of SAP versus MDI on HbA1c.

**Secondary endpoints** include:

- 1) Severe hypoglycemia
- 2) Change in body weight
- 3) Local reactions on the site of insulin administration and/or monitoring of glucose
- 4) Treatment satisfaction, measured using the Italian validated version of the WHO Diabetes Treatment Satisfaction Questionnaire.
- 5) Patients' preference for either treatment

## Study design

The study is designed as a single-center, open-label, cross-over randomized trial.

Lo studio è disegnato come un trial randomizzato in cross-over, in aperto.

After verification of inclusion and exclusion criteria, enrolled patients will be randomized (using a computer-generated random number sequence) 1:1 to either SAP or MDI for 4 months, and then switched to the alternative treatment.

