## **Statistical plan**

### **Determination of sample size.**

The sample will be composed of 27 patients. This will allow to reach a 80% power of detecting ( $p < 0.05$ ) a difference in HbA1c between groups > 0.5%, assuming a standard deviation of 0.83%.

Principal analysis (superiority): Variations of HbA1c in the two study phases will be compared using Student's paired t tests, which will also be used to compare end-of-treatment and baseline HbA1c for each treatment phase. A repeated measure linear regression model will be applied to compare the effects of the two treatments adjusting for treatment sequence. These analyses will be performed both by intention to treat (primary analysis), i.e. including all randomized patients and imputing missing data (if any) with the last observation carried forward (LOCF) method, and by protocol, i.e. restricted to patients actually using planned treatments.

Secondary endpoints: the same methods will be applied for analyses of secondary endpoints.

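### Only a 1:1 computer-generated sequence is specified, with no blocking stated; blocking treatment order and adding a period term would cheaply protect a 27-patient cross-over from an unlucky split

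*Combined protocol and SAP*

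**What the plan says.** The Study design section of the combined protocol and SAP describes a single-center, open-label cross-over in which "enrolled patients will be randomized (using a computer-generated random number sequence) 1:1 to either SAP or MDI for 4 months". Each patient later crosses to the other arm, so randomization fixes the order of treatments: sensor-augmented pump first or MDI first. The section neither describes nor excludes blocking, stratification or any other restriction, and it sets no target split between the two orders.

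Under Duration of the study, the phases are "4 months for each treatment phase, with no wash-out", and enrolment runs for 18 months.

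The Statistical plan says "The sample will be composed of 27 patients". Under the principal analysis, "Variations of HbA1c in the two study phases will be compared" with paired t tests. The same paragraph also plans a repeated-measures linear regression of the treatment effect with adjustment for treatment order. Period is not named as a term anywhere. The same methods are to be used for the secondary endpoints, which include satisfaction and preference.

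**The concern.** A two-period cross-over compares treatments within patients, but phase 1 and phase 2 can differ for reasons unrelated to treatment. If the two orders are equally frequent, such a period effect cancels from the mean treatment difference. If they are not, part of it remains unless the analysis removes it.

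Simple randomization gives equal numbers only on average, and with 27 patients a marked imbalance is not rare. The paired t test has no period term and so offers no protection.

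A period effect is plausible here. The trial is open-label, patients are trained to act on sensor readings during the pump phase, and phase 2 follows phase 1 directly. If change in HbA1c is measured from the start of each phase, any general improvement on entering the trial falls in phase 1 only. The documents give no estimate of its size.

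**Working it through.** **Inputs from the documents.** N = 27, difference 0.5% HbA1c, SD 0.83%, 80% power, p < 0.05 (Determination of sample size); 1:1 allocation (Study design). **Assumptions.** Simple randomization; a two-sided test; 0.83% is the SD of the within-patient difference (the plan does not say); a period effect π of 0.2 to 0.4% HbA1c.

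**1. The plan's own figure.** The normal approximation gives n = (0.83 × (1.960 + 0.842) / 0.5)² = 21.6, so 22. The exact paired t calculation gives 24 (power 80.7%), and 27 patients give 85.4%. So 27 is not reproduced exactly; 24/(1 − 0.10) = 26.7 would round to it, but no dropout rate is stated. This is a separate matter: the split probabilities below depend only on N = 27 and simple allocation.

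**2. Probability of an uneven split.** With X ~ Binomial(27, 0.5), P(split of k:(27 − k) or worse, either direction) = 2 × P(X ≤ k).

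**3. Share of the period effect in the paired mean.** Let τ be the treatment difference (pump minus MDI) and π the shift from phase 1 to phase 2. A pump-first patient has expected difference τ − π and an MDI-first patient τ + π. The mean over all patients is τ + π × (n_MDI-first − n_pump-first)/27, so the share is |n₁ − n₂|/27.

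**4. Variance cost once period is adjusted for.** Relative to 13:14, the variance ratio is (1/n₁ + 1/n₂)/(1/13 + 1/14).

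| Split | P(this or worse) | Share of π | Bias for π = 0.2 to 0.4 | Variance ratio |
|---|---|---|---|---|
| 13:14 | 100% | 1/27 = 4% | 0.01 | 1.00 |
| 10:17 | 24.8% | 7/27 = 26% | 0.05 to 0.10 | 1.07 |
| 9:18 | 12.2% | 9/27 = 33% | 0.07 to 0.13 | 1.12 |
| 8:19 | 5.2% | 11/27 = 41% | 0.08 to 0.16 | 1.20 |

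Averaged over simple allocation, the expected share is 15.5% in absolute size and the mean variance ratio is 1.04.

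**5. Scale.** The standard error of the paired mean is 0.83/√27 = 0.16. At 10:17, simulation (40,000 runs) gives the paired t test a type I error of 5.5% for π = 0.2, 5.9% for 0.3 and 7.0% for 0.5. Averaged over simple allocation, bias is zero and type I error is about 5%. With within-patient differences adjusted for order, bias at 10:17 is about 0, type I error about 5% and power about 83%, against about 85% at 13:14.

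**6. What balance alone does not do.** Even at 13:14, an unmodelled period effect adds to the spread of the differences. For π = 0.3 the simulated power is about 80% for the paired t test and 85% with adjustment for order. This is why the fix has two parts.

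**The case against.** The strongest objection is that the text does not say allocation is unblocked. A computer-generated 1:1 sequence can be simple or blocked, so the 24.8% is conditional on one reading. That stands. A reader might infer that the trial uses no blocking, but the documents show only that no restriction is stated.

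Second, the planned regression already adjusts for treatment order. If order is fitted to within-patient differences, the period effect is removed at any split. If it enters a repeated-measures model only as a main effect, it is constant within each patient and leaves the treatment contrast, with its share of the period effect, unchanged. The text does not settle which is meant, so the regression cannot be counted as protection, nor dismissed.

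Third, the size is modest and the period effect is assumed. A reader might infer a bias of up to a third of the 0.5% target (0.16). That needs both the top of the assumed range and an 8:19 split, which has about a 5% chance even under simple allocation. At 10:17 the bias stays below one standard error. Nor is the paired t test invalid, since over simple allocation as a whole it is unbiased with about the nominal error rate.

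Fourth, short blocks in an open-label, single-center trial can make the next allocation guessable. This is a real trade-off. It is small here because every patient receives both treatments, and varying block sizes and concealment reduce it further.

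**Conclusion.** The point holds as a cheap improvement. The stated method includes no restriction; followed literally, it carries about a one-in-four chance of a 10:17 or worse split. At that split a quarter of any period effect enters the first-listed principal test. For an assumed period effect of 0.2 to 0.4%, the bias is 0.05 to 0.10% HbA1c against a standard error of about 0.16. Where period is adjusted for, the cost of that split is about 7% in variance (about 4% on average over simple allocation), or at most one to two points of power.

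The conclusion rests on simple randomization, on all 27 patients contributing, and on reading 0.83% as the SD of the within-patient difference. Only the standard error and power figures depend on the last. Effects on satisfaction, preference and balance over calendar time were not quantified and add no weight here.

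**What to change.** In Study design, replace the description of the sequence with: a computer-generated list of treatment orders in permuted blocks of randomly varying size (2 and 4), prepared by someone not involved in enrolment and concealed until the patient is entered. Complete blocks are balanced, and an unfinished last block leaves the orders one apart at 27, so the split is 13:14 if all 27 are randomized. If a blocked list is already intended, saying so is enough.

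In the Statistical plan, name period as a term, alongside treatment and sequence, in the repeated-measures model.

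The cost is one sentence in each section and a different list-generation command, with no added patients or visits. The downside is some remaining predictability of the next allocation. Neither change addresses carry-over between phases.

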## Treatments

- **MDI:** multiple daily injections of insulin, using degludec as basal insulin and lispro, aspart or glulisine as prandial insulin. Dose adjustments will be performed on the basis of self-monitoring of capillary blood glucose (standard of care).
- **SAP:** Sensor augmented pump Vibe Animas Platinum integrated with glucose sensor Dexcom G4. Patients will be educated to manage glucose excursions detected by the sensor, and instructed to download sensor and pump data before each planned visit.

## Duration of the study

- *Duration of enrolment:* 18 months
- *Duration of treatment:* 4 months for each treatment phase, with no wash-out.

## Study population

**Setting:** Outpatients with type 1 diabetes referring to the Diabetes Clinic of SODc Diabetologia, AOU-Careggi, [name].

## **Inclusion criteria**

1. Written informed consent
2. Diagnosis of type 1 diabetes, with a duration of diabetes of at least 2 years
3. Age 18-75 years
4. Current treatment with basal-bolus insulin, using a fast acting analog (lispro, aspart, glulisine) as prandial insulin and a long-acting analog (glargine, detemir or degludec) as basal insulin.
5. HbA1c < 8.0% (64 mmol/mol)
6. No severe diabetic complications (blindness for diabetic retinopathy, severe renal failure, lower extremity amputations)
7. Reported frequency of self-monitoring of blood glucose of at least 4 daily, with a meter allowing the download of data in electronic format

## **Exclusion criteria**

1. HbA1c > 8.0% (64 mmol/mol)
2. Duration of diabetes > 2 years
3. Uncompensated mental disorders
4. Pregnancy or lactation, or planned pregnancy within six months of enrolment
5. Any condition with a life expectancy < 1 year

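### Exclusion criterion 2 bars diabetes of more than 2 years while inclusion criterion 2 requires at least 2 years, so as written essentially nobody is eligible

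*Combined protocol and SAP*

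**What the plan says.** Three places in the combined protocol and SAP bear on this.

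- **Inclusion criteria, item 2:** "Diagnosis of type 1 diabetes, with a duration of diabetes of at least 2 years".
- **Exclusion criteria, item 2:** "Duration of diabetes > 2 years".
- **Study design:** "After verification of inclusion and exclusion criteria, enrolled patients will be randomized". Both lists are therefore conditions for randomization, and neither takes precedence over the other.

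No other section defines how duration is measured, qualifies either criterion, or says which one prevails if they conflict. The target for recruitment is in the sample size paragraph: "The sample will be composed of 27 patients".

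**The concern.** The two duration rules point in opposite directions from the same cut-off. The patients that the inclusion list demands are, apart from a single point, the patients that the exclusion list removes. Eligibility criteria are operative text: they decide who is randomized, and they are what a monitor, an ethics committee or a later reader checks the enrolled patients against.

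There are three ways the text could be used in practice.

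1. Both rules are applied. Recruitment of 27 patients is then effectively impossible.
2. The inclusion rule is applied and the exclusion is disregarded. Every enrolled patient with a duration above 2 years is then ineligible on the face of the protocol.
3. The exclusion is applied and the inclusion rule is disregarded. The trial then enrols patients diagnosed within the last 2 years, a population that meets the one described by inclusion 2 only at exactly 2 years.

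In none of the three does the protocol itself tell a reader which population the trial was meant to study.

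**Working it through.** The plan gives no figure to reproduce here, and the point does not depend on the power, significance level or standard deviation. It is a check of two sets. Let *d* be diabetes duration in years.

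**Inputs**

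- Inclusion 2 admits *d* ≥ 2.
- Exclusion 2 removes *d* > 2, so it leaves *d* ≤ 2.
- Study design: both must hold before randomization.

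**Eligible set**

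{*d* ≥ 2} ∩ {*d* ≤ 2} = {*d* = 2}

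**Check at particular durations**

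| Duration (years) | Meets inclusion 2 | Caught by exclusion 2 | Eligible |
|---|---|---|---|
| 1 | no | no | no |
| 1.99 | no | no | no |
| 2.0 | yes | no | yes |
| 2.01 | yes | yes | no |
| 5 | yes | yes | no |
| 20 | yes | yes | no |

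**Sensitivity to how duration is recorded.** The documents give no rule. If duration were counted in completed years (an assumption), a patient at any point from 2 to just under 3 years would be recorded as 2 and would pass both criteria. The window is then one year wide: still narrow, and still not the open-ended group that inclusion 2 describes.

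**Comparison with the HbA1c pair.** Inclusion 5 admits HbA1c below 8.0% and exclusion 1 removes HbA1c above 8.0%. Together they give {< 8.0} ∩ {≤ 8.0} = {< 8.0}, so that exclusion repeats the inclusion limit from the other side and changes nothing. If exclusion 2 carried the opposite sign, the duration pair would behave in the same way: {*d* ≥ 2} ∩ not {*d* < 2} = {*d* ≥ 2}. With the sign as printed, the pair cancels.

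**Number affected.** With both rules in force, effectively 0 of the planned 27 can be enrolled. With inclusion 2 alone in force, up to 27 of 27 breach exclusion 2.

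**The case against.** The strongest reply is that this is an obvious slip. The inclusion limit is spelled out in words, the exclusion turns on one symbol, and site staff would notice the conflict and apply the inclusion rule. The third scenario above, in which they ignore an explicit inclusion criterion, is the least likely. It can also be said that no result changes. The Statistical plan defines intention to treat by randomization and the per-protocol set by use of the planned treatments, so a breach of exclusion 2 removes nobody from either analysis.

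Much of this is right, and it limits the consequences. The planned analysis sets are unaffected. No bias in the treatment comparison is claimed.

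Some supporting points also need care. The case for a reversed sign rests on one parallel pair. Exclusions 3 to 5 mirror nothing in the inclusion list, and even the HbA1c pair is not an exact complement, since a value of exactly 8.0% is in neither criterion. The text was also read from PDF by a program, so a misread symbol cannot be ruled out without the source page. Nothing suggests one, however: both inequality signs appear elsewhere in the same exclusion list and make sense there.

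What the reply does not do is make the text usable. If staff rely on the presumed intent, they enrol patients whom the protocol says to exclude, and the protocol contains nothing to justify that choice.

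**Conclusion.** The concern holds. Inclusion 2 and exclusion 2 contradict each other in current, operative text, and no other section resolves the conflict. Taken literally, the eligible population is the single point of exactly 2 years, or durations from 2 to under 3 years if completed years are recorded. Neither is a workable basis for recruiting 27 patients or matches the group described by inclusion 2.

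The contradiction rests on no statistical assumption. That the sign in exclusion 2 was reversed is the likeliest explanation, but it is an inference that only the sponsor can confirm. The harm falls on recruitment, on verification of eligibility and on the definition of the study population, not on the planned analyses. It must be corrected because the criteria cannot be followed as written.

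**What to change.** Reconcile the two criteria by amendment. Assuming inclusion 2 expresses the intended population, there are two equivalent ways:

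- reverse the inequality in exclusion 2, so that it removes a duration below 2 years and becomes the complement of inclusion 2; or
- delete exclusion 2, since inclusion 2 already sets the limit.

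It would help to state in the same amendment how duration is counted, for example from the date of diagnosis to the screening visit, so that the boundary is unambiguous.

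The text change is one character or one deleted line, and it leaves the design, the sample size and the analysis untouched. The remaining cost is the handling of the amendment. The documents do not say whether enrolment has begun; if it has, the eligibility records of patients already randomized should be checked against the corrected criterion and the outcome recorded.
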